The BRAIN App: Building Relationships Using Artificial Intelligence and Nostalgia NCT05515679

Study Protocol 7/27/22

STUDY OVERVIEW

Study Title:

The BRAIN App: Building Relationships using Artificial Intelligence and Nostalgia

This is a quasi-experiment using a pre-post design—i.e., baseline vs. treatment / post-treatment. The study investigates the effects of an Artificial Intelligence-enabled Cognitive Stimulation Therapy (CST) app on persons with dementia (PWD). The primary objective is to examine the impact of the app on engagement / affect. More specifically, the study will examine whether the app produces increases in Constructive Engagement, Passive Engagement, and Pleasure and/or decreases in Other Engagement, Non-Engagement, and Anxiety/Sadness. A secondary objective is to examine the impact of the app on quality of life, neuropsychiatric symptoms, and the quality of the carer-patient relationship.

This study will be conducted at one CCRC, in their nursing home (NH) and assisted living facility (ALF). The study will involve 24 PWD (12 from a NH and 12 from an ALF), 20 staff members (10 from a NH and 10 from an ALF), and 24 family members (12 related to PWD from a NH and 12 related to PWD from an ALF). PWD will be 65+ years old, diagnosed with any type of dementia, and speak and read English. In addition, the exhibit at least one responsive behavior at baseline, based upon the NPI-NH (Neuropsychiatric Inventory-Nursing Home) and/or score below the maximum on the Dementia Quality of Life (DEMQOL) scale. To accommodate for attrition, 28 PWD, 24 Staff Members, and 28 Family Members will initially enroll in the study.

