 - b. He/she is able to read and speak English

PLEASE NOTE: The above screening process will occur 1-30 days after the consent is signed

Screening Log

After completing the screening process, the researcher will enter data into the Screening Log. The Screening Log will be digital in nature (a spreadsheet) include the following information: the individual's initials, identification number (screening number), age, gender, race, ethnicity, screening date, and eligibility status. (e.g., eligible for study participation and date enrolled; ineligible for study participation and reason; refused consent and reason). The file will be saved on the Hopeful Aging servers.

A screenshot of the study's Screening Log with sample data entered is included in the Appendix.

Eligibility Criteria Inclusion Criteria

PWD

PWD must reside in an ALF or NH, be 65+ years old, diagnosed with any type of dementia, speak and read English, and exhibit at least one responsive behavior at baseline, based upon the NPI-NH (Neuropsychiatric Inventory-Nursing Home).

Staff Members

Staff Members must be at least 18 years old and speak and read English.

Family Members

Family Members must be at least 18 years old and speak and read English.

Exclusion Criteria

PWD will be excluded if they are bed confined, completely unable to communicate verbally, have serious visual or hearing impairments and/or show signs of rapid cognitive decline or physical deterioration over the last 6 months, as evidenced by medical records.

Staff Members will be excluded if they only work third shift (e.g., 11pm – 7am).

Family Members will be excluded if they indicate that they have no knowledge of their loved one's background.

STUDY INTERVENTION

All PWD will receive the same intervention. Namely, they will take part in one-on-one activity programming for four weeks, using the BRAIN app three times per week. Each activity session will last 15-25 minutes and be led by a professional care partner (CP—e.g., nursing assistant, caregiver, activity professional, etc.).

The total length of participation in the study for persons with dementia will be three months, including one month for baseline, one month for the intervention period, and about two weeks for post-treatment.

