a. Researchers will observe PWD's engagement and affect during standard, staff-led activities using the MPES (Camp, Skrajner, & Gorzelle, 2015). The MPES is an observational scale that measures four types of engagement: Constructive Engagement: motor/verbal behavior exhibited clearly in response to the target activity; Passive Engagement: listening/watching a target activity; Distracted Engagement: motor/verbal behavior exhibited in response to something other than the target activity; and Non-Engagement / Apathy: outward signs/indicators of apathy, such as sleeping, closing one's eyes, and staring into space. The MPES also measures Pleasure, defined as clearly observable smiling or laughing. Each observation period lasts five minutes, with multiple observations taken on each participant. To ensure MPES data provides a robust comparison for treatment programming, each participant will be observed at least 12 times, so that averages can be calculated for each type of engagement/affect

5. Observations of PWD in Standard Activities w/ EPWDS

- a. Participants will also be observed at baseline using the EPWDS (Jones et al., 2018). This scale measures engagement in 5 domains: affective, visual, verbal, behavioral, and social. At least 12 EPWDS observations will be taken for each participant, to enable calculation of average scores.
- b. Each item on the scale is scored on a scale of 1 (Strongly Disagree) to 5 (Strongly Agree)

PLEASE NOTE: all of the above measures will be completed 8-30 days after the informed consent document and assent form are signed.

Intervention Period Data Collection

1. Treatment Fidelity / Process Measures

- a. The PWD will be invited to participate in three BRAIN sessions per week for four weeks. A Session Summary Form will be completed for each scheduled session, even if the session does not actually occur due to the PWD's unavailability or refusal to participate. The following data will be collected on the Session Summary form:
 - i. PWD ID#
 - ii. Date of Session
 - iii. Time of Session
 - iv. Facilitator ID#
 - v. Did the PWD attend the session? (Yes/No)
 - 1. If NO to previous question, please indicate why the PWD did not attend? (Unavailable / Refused / Other)
 - 2. Reason for unavailability or refusal
 - vi. Length of Session

2. Observations of PWD in BRAIN Sessions w/ MPES

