1. OCPR

- a. A researcher will conduct a direct interview with the staff member to conduct the OCPR.
- b. The QCPR is a 14-item scale measures warmth and/or absence of conflict or critique on a 5-point Likert scale, ranging from "totally disagree" to "totally agree."
 - i. For warmth/affection items, "totally disagree" responses are scored with one point and "totally agree" responses are scored with five points. Intermediate responses are scored with two, three, or four points.
 - ii. For conflict/criticism items, "totally agree" responses are scored with one point and "totally disagree" responses are scored with five points. Intermediate responses are scored with two, three, or four points.
 - iii. A score under 42 reflects a poor relationship, while a score over 56 reflects a good relationship. The remaining scores (between 42 and 56) indicate that the quality of the relationship is common, i.e., a standard relationship (Spruytte et al., 2002).

2. Pre-Training Quizzes for Training Modules

- a. Staff will be asked to complete two 15-item quizzes--i..., one 15-item quiz for "Training Module 1: Using the BRAIN App" and one 15-item quiz for "Training Module 2: Top 10 Tips for Facilitating Activities with Persons with Dementia."
- b. All questions will be multiple choice in nature.
- c. Staff will complete the quizzes independently on a computer, tablet, or smartphone

PLEASE NOTE: the above measures will be completed 8-30 days after the informed consent document is signed.

Intervention Period Data Collection

1. Take Two Training Modules

- a. During the first week of the Intervention Period, the staff member will take the two online training modules:
 - i. Training Module 1: Using the BRAIN App
 - ii. Training Module 2: Top 10 Tips for Facilitating Activities with Persons with Dementia

2. Learning Management System Automatically Collects Basic Training Data

- a. The Learning Management System will automatically collect two pieces of data for each training module:
 - i. Did the Staff Member complete the training module? (Yes/No)
 - ii. How long did it take for the Staff Member to complete the training module (in minutes)?

3. Post-Training Quizzes for Training Modules

a. After completing each training module, the Staff Member will be presented with the two 15-item quizzes that were presented to them at baseline (although the order of the questions will be changed).

4. Treatment Fidelity / Process Measures

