The BRAIN App: Building Relationships Using Artificial Intelligence and Nostalgia
NCT05515679

Statistical Analysis Plan 7/27/22

The BRAIN app will be considered successful if persons with dementia exhibit higher levels of positive engagement/affect and lower levels of negative engagement--as measured by the Menorah Park Engagement Scale (MPES) and Engagement of Persons with Dementia scale (EPWDS)--during the intervention, as compared to standard programming at baseline. First, multiple observations of participants will be taken at both baseline and treatment on both scales. Then, means will be calculated for each participant for each item (on the MPES) or positive and negative subscale (for the EPWDS). Then, we will conduct a paired sample *t*-test to determine whether there are significant differences from baseline to treatment. We will also conduct paired sample *t*-tests to examine whether participants exhibit an improvement in quality of life (based upon the DEMQOL) and) a reduction in responsive behaviors (based upon the NPI-NH).

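### The SAP credits the app with a difference that the design can attribute only to the whole BRAIN package compared with standard programming

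*Protocol*

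**What the plan says.** **Aim and design.** The Protocol's Study Overview states: "The primary objective is to examine the impact of the app on engagement / affect". It describes the design plainly: "This is a quasi-experiment using a pre-post design". Under Study Intervention, "All PWD will receive the same intervention", so there is no concurrent comparison.

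**Intervention period.** The same section says of the residents that "they will take part in one-on-one activity programming for four weeks". Sessions use the app three times a week, last 15-25 minutes and are led by a care partner. Staff take two modules, one on operating the app (about 15 minutes) and one on good practice in leading activities for people with dementia (about 30 minutes). The second is not specific to the app. On timing, the Staff Members part of Study Measurements and Procedures says: "During the first week of the Intervention Period, the staff member will take the two online training modules".

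**Baseline period.** Under the PWD Baseline Assessments / Observations, "Researchers will observe PWD's engagement and affect during standard, staff-led activities using the MPES". The EPWDS is also completed at baseline. Each scale is completed at least 12 times per resident and averaged. Neither this section nor Visit Procedures says whether the baseline activities are group or individual, how many residents attend, how long they last or who leads them.

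**Success rule.** The SAP reads: "The BRAIN app will be considered successful if persons with dementia exhibit higher levels of positive engagement/affect and lower levels of negative engagement", measured on the MPES and EPWDS and compared with standard programming at baseline. The test is a paired t-test on each resident's period means, with no term for activity format or facilitator.

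**The concern.** Between baseline and intervention, more changes than the presence of the app. Delivery in the intervention period is one-on-one, and the staff have just been taught general facilitation skills. Both could move the outcomes without the app. The MPES scores whether a resident responds to, watches, is distracted from or ignores a target activity, and the EPWDS includes verbal and social domains. A resident alone with a facilitator plausibly gets more prompts and meets fewer distractions than one in a group.

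The stake is the trial's main conclusion. Followed as written, the SAP could report that the app works when the data show only that the package differs from usual programming. A site deciding whether to buy the app, or instead to train staff and schedule individual sessions, would be misled about which of these had been tested.

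**Working it through.** **Step 1. Is there a figure to reproduce?** No. The documents state no significance level, sidedness, power, effect size or SD, so the calculation below is an illustration.

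**Step 2. What differs between the two periods?**

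| Component | Baseline | Intervention |
|---|---|---|
| App | absent | present |
| Format | not stated | one-on-one |
| Session length | not stated | 15-25 minutes |
| General facilitation training | on the schedule, not yet taken | taken in the first week |
| Session Summary Form (facilitator, length) | not listed | listed for every scheduled session |

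For one resident and one endpoint, let D be the treatment mean minus the baseline mean. Then

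E[D] = app effect + training effect + format effect + any change over time.

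The format effect is zero if the baseline activities are already one-on-one. No arm, period or covariate separates the terms, so the paired t-test estimates their sum. Taking 12 or more observations per period reduces the noise in D but leaves this sum unchanged.

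**Step 3. How easily could the test be significant with no app effect?**

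Inputs:
- n = 24 residents (Study Overview), with 28 enrolled to allow for attrition.
- Assumed two-sided level of 0.05.
- Assumed app effect of zero.
- Assumed shift from format and training of d SDs of the paired difference.

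The statistic T = mean(D) / (SD(D)/√n) follows a noncentral t distribution with n − 1 = 23 degrees of freedom and noncentrality λ = d√24 = 4.899d. The critical value is 2.069, so an observed d of 2.069/4.899 = 0.42 is enough for significance.

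| d from format/training | λ | P(significant, favourable), n = 24 | same, n = 28 |
|---|---|---|---|
| 0 | 0 | 2.5% | 2.5% |
| 0.3 | 1.47 | 29% | 33% |
| 0.5 | 2.45 | 65% | 72% |
| 0.6 | 2.94 | 80% | 86% |

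A simulation at n = 24 with 100,000 replicates agreed (29% at d = 0.3, 65% at d = 0.5).

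**Step 4. Does the test respond to the app's share of the effect?** Suppose the total is d = 0.8. One endpoint is then significant 96% of the time, whatever the app's share. Now take a within-person comparison that isolated the app, assuming the same SD of the paired difference. If format and training explained 25%, 50%, 75% or 100% of the total, the app's part would be d = 0.6, 0.4, 0.2 or 0. That comparison would be significant 80%, 47%, 15% or 2.5% of the time. The planned test cannot tell these cases apart.

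**The case against.** The strongest reply is that the documents already define a package. Study Intervention describes individual sessions with the app led by a care partner, and presents both modules as preparation for delivering the BRAIN intervention. The SAP names standard programming as its comparator. The design is openly called a quasi-experiment, and a small single-group study is not expected to separate components. This is a fair reading, and it is why no additional arm is asked for. But the objective and the success statement both name the app, and neither document limits what may be attributed to it. If the package is meant, the text should say so.

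The reply also rules out several stronger readings that a reader might infer:

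- *Baseline format is unrecorded, so the problem could never be checked.* Not shown. The Protocol places the MPES and EPWDS forms in an Appendix that is not in the text available here, and they may carry such fields. The Session Summary Form is a fidelity form, so its absence at baseline does not settle the matter.
- *Format is completely confounded with the app.* Not established. Nothing says that baseline activities are group activities. If all were one-on-one, the format part would vanish and the training difference would remain.
- *Any gain counts as success.* No. The SAP tests for significant differences.
- *Restricting the baseline to one-on-one observations would isolate the app.* No. Facilitation at baseline would still, on the schedule, precede training.

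**Conclusion.** The point holds in this form: a positive result would support the package over standard programming, and would not support a claim for the app alone. This follows from the two documents and needs no assumed number. The format part of the confounding depends on what the baseline activities turn out to be. The training part follows from the schedule of modules, although staggered enrolment could mean that some staff are already trained when they lead a later resident's baseline activity.

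The 29%, 65% and 80% rest on an assumed level and on assumed shifts of 0.3, 0.5 and 0.6. Nothing in the documents suggests how large such a shift would be. A reader might take these figures as the chance of wrongly declaring success. They are not: each refers to one endpoint, while the success rule spans positive and negative engagement on two scales, and the chance of meeting all of it could be lower.

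The study can run as designed. Its headline claim should be brought into line with what it compares.

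**What to change.** 1. Reword the Protocol objective and the SAP success statement so that the effect tested is *one-on-one BRAIN sessions led by trained staff versus standard programming*. This costs nothing beyond a narrower claim.
2. Check the Appendix MPES and EPWDS forms. Unless they already do so, record for each baseline observation the activity format (group or one-on-one, and number of residents), the activity type and the Facilitator ID. This adds three fields to forms that researchers already complete, and no sessions.
3. Pre-specify a descriptive sensitivity comparison of the intervention means with the one-on-one or smallest-group baseline observations that occur naturally in usual programming. Do not change which activities are sampled, because adding individual sessions would alter the comparator named in the SAP. State that this comparison does not remove the training difference, and that it may rest on few observations or none.

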1. BIMS

- a. A researcher will conduct a direct interview with the PWD to conduct the BIMS.
- b. The BIMS is a structured evaluation aimed at evaluating aspects of cognition in elderly patients. The BIMS assesses patient attention, level of orientation, and ability to recall information. There are three assessment stages in the BIMS assessment:
 - i. During part I, the patient is asked to repeat three words that are to be given by the assessor. The accuracy of the word reproduction is assessed. Also, the patient is informed that they will need to remember the words at a later moment during the evaluation.
 - ii. During part II, temporal orientation is evaluated by asking the patient to recall temporary coordinates (current year, month and day of the week). These are to be asked in separate questions and about 30 seconds are to be given for response.
 - iii. During part III the patient is asked to recall the three words given in part I. If needed, cues may be given after waiting for 5 seconds for spontaneous recall.

- c. Each of the seven items that BIMS consists of, is awarded a number of points ranging from 0 to 3. The higher the score, the lower the impairment to the cognitive response. Scores closer to 0 indicate severe cognitive impact whilst scores closer to 15 indicate an intact cognitive response
 - i. Score Interpretation

0 - 7 Severe cognitive impact

8 - 12 Moderate impairment

13 - 15 Intact cognitive response

2. DEMQOL

- a. A researcher will conduct a direct interview with the PWD to conduct the DEMQOL. However, if the PWD is unable to respond to questions on the DEMQOL, this measure will be collected via proxy interview (with a staff member who is familiar with the PWD.
- b. The DEMQOL is a 28-item self-reported measure related to health-related quality-of-life (HRQL) in patients with dementia. The DEMQOL takes cognition, negative emotion, positive emotion, social relationships, and loneliness into consideration. The DEMQOL-Proxy is a 31-item test completed by the caretaker and focuses on cognition, negative emotion, positive emotion, daily activities, and appearance.
 - i. Each item on the DEMQOL (and DEMQOL-Proxy) has four options:

Not at all

A Little

Ouite a Bit

A Lot

ii. Most items are scored as follows

Not at all = 4

A Little = 3

Quite a Bit =2

A Lot=1

iii. However, since some questions are worded differently, they are reverse coded in the following manner:

Not at all = 4

A Little = 3

Quite a Bit =2

A Lot=1

- iv. The total possible score on the DEMQOL ranges from 28 112, with lower scores indicating a lower quality of life.
- v. There is also a 29th item on the DEMQOL, which asks the PWD to rate his/her overall quality of life. this item has the following options and coding:

Poor = 1

Fair = 2

Good = 3

Very Good = 4

vi. This final item is not included in the total score on the DEMQOL

3. Document All Diagnoses, Type of Dementia, Meds, and Demographics

a. A researcher will conduct a CHART REVIEW to collect the following data:

- i. All diagnoses
- ii. Type of dementia
- iii. All meds
- iv. Demographics (race/ethnicity, education level, marital status, and number of years living in LTC)

4. Observations of PWD in Standard Activities w/ MPES

a. Researchers will observe PWD's engagement and affect during standard, staff-led activities using the MPES (Camp, Skrajner, & Gorzelle, 2015). The MPES is an observational scale that measures four types of engagement: Constructive Engagement: motor/verbal behavior exhibited clearly in response to the target activity; Passive Engagement: listening/watching a target activity; Distracted Engagement: motor/verbal behavior exhibited in response to something other than the target activity; and Non-Engagement / Apathy: outward signs/indicators of apathy, such as sleeping, closing one's eyes, and staring into space. The MPES also measures Pleasure, defined as clearly observable smiling or laughing. Each observation period lasts five minutes, with multiple observations taken on each participant. To ensure MPES data provides a robust comparison for treatment programming, each participant will be observed at least 12 times, so that averages can be calculated for each type of engagement/affect

5. Observations of PWD in Standard Activities w/ EPWDS

- a. Participants will also be observed at baseline using the EPWDS (Jones et al., 2018). This scale measures engagement in 5 domains: affective, visual, verbal, behavioral, and social. At least 12 EPWDS observations will be taken for each participant, to enable calculation of average scores.
- b. Each item on the scale is scored on a scale of 1 (Strongly Disagree) to 5 (Strongly Agree)

PLEASE NOTE: all of the above measures will be completed 8-30 days after the informed consent document and assent form are signed.

Intervention Period Data Collection

1. Treatment Fidelity / Process Measures

- a. The PWD will be invited to participate in three BRAIN sessions per week for four weeks. A Session Summary Form will be completed for each scheduled session, even if the session does not actually occur due to the PWD's unavailability or refusal to participate. The following data will be collected on the Session Summary form:
 - i. PWD ID#
 - ii. Date of Session
 - iii. Time of Session
 - iv. Facilitator ID#
 - v. Did the PWD attend the session? (Yes/No)
 - 1. If NO to previous question, please indicate why the PWD did not attend? (Unavailable / Refused / Other)
 - 2. Reason for unavailability or refusal
 - vi. Length of Session

2. Observations of PWD in BRAIN Sessions w/ MPES

a. Researchers will observe PWD's engagement and affect during BRAIN sessions using the MPES (Camp, Skrajner, & Gorzelle, 2015). The MPES is described above. Each participant will be observed at least 12 times during the intervention period, so that averages can be calculated for each type of engagement/affect.

3. Observations of PWD in BRAIN Sessions w/ EPWDS

a. Participants will also be observed at baseline using the EPWDS (Jones et al., 2018). The EPWDS is described above. At least 12 EPWDS observations will be taken for each participant during the intervention period, to enable calculation of average scores.

4. Satisfaction Questions

- a. At the end of each session a researcher will pose the following three questions to the PWD:
 - i. Did you enjoy the activity? Yes/No
 - ii. Would you do an activity like this again sometime? Yes/No
 - iii. Would you recommend this activity to others? Yes/No

PLEASE NOTE: all the above measures will be completed during the Intervention Period, which occurs 31-60 days after the informed consent document and assent form are signed.

Post-Treatment Assessments

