Brief Interview for Mental Status (BIMS) (Direct Interview)		X			
Dementia Quality of Life (DEMQOL) (Direct Interview or Proxy if unable to respond)		X			
Document All Diagnoses, Type of Dementia, Meds, and Demographics (Chart Review)		X			
Observations of PWD in Standard Activities w/ Menorah Park Engagement Scale (MPES)		X			
Observations of PWD in Standard Activities w/ Engagement for PWD Scale (EPWDS)		X			
Treatment Fidelity / Process Measures			X		
Observations of PWD during BRAIN activities using the MPES			X		
Observations of PWD during BRAIN activities using the EPWDS			X		
Satisfaction Questions			X		
DEMQOL (Direct Interview or Proxy, if PWD unable to respond)				X	
NPI-NH (Proxy Interview)				X	

Staff Members Timeline and Visit Schedule				
Assessment / Interview / Data to Collect	Screening (Days 1-7)	Baseline Interview, Chart Review, and Observations (Days 8-30)	Treatment Visits (Days 31-60, three visits per week)	Post-Treatment Interview (Days 61-74)
Informed Consent Form	X			
Confirm Age 18+ (Direct Interview)	X			
Confirm Read & Speak English (Direct Interview)	X			
Confirm Staff Does Not Only Work Third Shift (Direct Interview)	X			
Enrollment (if eligible)	X			
Quality of Carer-Patient Relationship (QCPR)		X		
Pre-Training Quizzes for Training Modules		X		
Take Two Training Modules			X	
Learning Management System Automatically Collects Basic Training Data			X	
Post-Training Quizzes for Training Modules			X	
Treatment Fidelity / Process Measures			X	
Satisfaction Questions			X	
Quality of Carer-Patient Relationship (QCPR)				X

Family Members Timeline and Visit Scheudle			
Assessment / Interview / Data to Collect	Baseline & Screening (Days 1-30)		
Informed Consent Form	X		
Confirm Age 18+ (Direct Interview)	X		
Confirm Read & Speak English (Direct Interview)	X		
Enrollment (if eligible)	X		
Life Story Questionnaire	X		

VISIT PROCEDURES

PWD

Screening Procedures

Chart Review for Eligibility Criteria

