After consent is obtained from the PWD's legally authorized representative and the PWD him/herself provides assent, a researcher will schedule a time with staff at the nursing or assisted living to review eligibility information in his/her chart (i.e., age 65+, able to read and speak English, diagnosed with dementia (of any type), NOT bed confined, NOT completely unable to communicate verbally, does NOT have serious visual or hearing impairments, and does NOT show signs of rapid cognitive decline or physical deterioration over the last 6 months).

NPI-NH Interview

A researcher will then schedule a time to interview a staff member familiar with the PWD to conduct the NPI-NH. The researcher will follow standard protocol for conducting the NPI-NH and be extensively trained on how to properly use the measures.

Baseline Procedures

Baseline Assessment

A researcher will schedule a time to work with the PWD and conduct a direct interview with him/her to complete the DEMQOL and BIMS. The researcher will follow standard protocol for conducting these measures and be extensively trained on how to properly use these measures. *Please note that the BIMS is not an outcome measure. The BIMS is exclusively being conducted so that we can describe the level of impairment of the study sample.*

Chart Review

A researcher will schedule a time with staff at the nursing or assisted living to collect the following data from his/her chart:

- All diagnoses
- Type of dementia
- All meds
- Demographics (race/ethnicity, education level, marital status, and number of years living in LTC)

Observations of Standard Activities

Researchers will observe the PWD taking part in standard activities using the MPES and EPWDS. At least 12 observations will be taken with each measure, so that an average score can be calculated for baseline, standard activity programming. Researchers will follow the standard protocols for using the MPES and EPWDS and be extensively trained on how to properly use these measures.

Intervention Period Procedures

The PWD will be invited to participate in three BRAIN sessions per week for four weeks. The sessions will be facilitated by a staff member at the nursing home or assisted living facility. The staff member will be trained on how to conduct BRAIN Sessions.

Treatment Fidelity / Process Measures

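### The DEMQOL may be self-report at one visit and proxy at the other, and no visible rule keeps the form or informant the same for the paired t-test (minor)

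*Protocol*

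**What the plan says.** The Study Overview makes this a secondary matter: "A secondary objective is to examine the impact of the app on quality of life".

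In the protocol's Baseline Assessments / Observations, the DEMQOL item makes direct interview the default and adds a fallback: "However, if the PWD is unable to respond to questions on the DEMQOL, this measure will be collected via proxy interview". The proxy respondent is a staff member who knows the PWD. The same item describes the second instrument: "The DEMQOL-Proxy is a 31-item test completed by the caretaker and focuses on cognition, negative emotion, positive emotion, daily activities, and appearance". The self-report form has 28 items, and its listed domains include social relationships and loneliness, where the proxy form has daily activities and appearance.

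Post-Treatment Assessments repeats the fallback condition without referring to the form used at baseline. The PWD visit schedule allows both routes at both visits; its post-treatment row reads "DEMQOL (Direct Interview or Proxy, if PWD unable to respond". The Visit Procedures section mentions only the direct interview at each visit.

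The SAP plans a paired t-test for "improvement in quality of life (based upon the DEMQOL") and does not mention the proxy form.

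**The concern.** A paired t-test assumes that each difference is a change on one scale. Here the two members of a pair may come from forms that differ in length, content and respondent. The condition is tested again at post-treatment with direct interview as the default, so the text allows switches both ways. A PWD who loses the ability to respond goes from self to proxy. A PWD on proxy at baseline who can answer on the later day goes from proxy to self, although that switch could be avoided. Proxy-to-proxy pairs may also change informant.

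A form that was not administered at a visit cannot be recovered in the analysis, so the rule has to be in place when the data are collected. What is at stake is how interpretable the quality-of-life comparison is among a planned 24 PWD.

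**Working it through.** **Inputs from the documents.** 28 self-report items and 31 proxy items, each with four options, scored 1 to 4 (DEMQOL item); 24 PWD (Study Overview); baseline on days 8–30 and post-treatment on days 61–74 (visit schedule).

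**The plan's own figure.** "The total possible score on the DEMQOL ranges from" 28 to 112. Check: 28 × 1 = 28 and 28 × 4 = 112. The stated total fits the self-report form.

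**Shift from form length.** At the same item mean m on both forms, a self-to-proxy switch changes the total by 31m − 28m = 3m:

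- m = 2.5: +7.5
- m = 3: +9
- m = 3.5: +10.5

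A proxy-to-self switch gives the same shift with the opposite sign.

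**Shift when raters also differ.** If the proxy item mean is d lower and m = 3, the shift is 31(3 − d) − 84 = 9 − 31d:

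- d = 0.2: +2.8
- d = 0.4: −3.4

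The sign depends on d, which the documents do not give, so the net direction is unknown.

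**Effect on the mean difference.** At +9 per switcher, one switcher moves the mean by 9/24 = 0.375 points and two move it by 18/24 = 0.75.

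**Effect on the test.** Simulation of a two-sided 5% paired t-test with n = 24, normal changes, no true change and m = 3. The 5% level, the SD of change and the number of switchers are assumptions. All switches are self-to-proxy.

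| Switchers | d | SD of change | False improvement | False worsening | Total |
|---|---|---|---|---|---|
| 1 | 0 | 10 | 3.5% | 1.5% | 5.0% |
| 2 | 0 | 10 | 4.8% | 0.9% | 5.7% |
| 2 | 0 | 8 | 5.4% | 0.7% | 6.0% |
| 2 | 0 | 12 | 4.4% | 1.1% | 5.5% |
| 2 | 0.2 | 10 | 3.2% | 1.9% | 5.1% |
| 2 | 0.4 | 10 | 1.8% | 3.3% | 5.1% |

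Totals may differ from the sum of the parts by rounding. The total error stays close to nominal; what changes is the balance between the two tails.

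**How likely is a switch?** The two assessments are 61 − 30 = 31 to 74 − 8 = 66 days apart. The exclusion criteria remove PWD who are "completely unable to communicate verbally, have serious visual or hearing impairments and/or show signs of rapid cognitive decline or physical deterioration". Both facts suggest few switches, but no rate can be derived. No cognitive floor is set, so PWD on the border of being able to self-report remain eligible.

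**Would per-item scoring solve it?** Dividing each total by its number of items and rescaling to 28 items gives a shift of −28d in place of 9 − 31d. The two are equal in size when 28d = 9 − 31d, that is d = 9/59 ≈ 0.15, and above that per-item scoring gives the larger shift. At d = 0.2, +2.8 becomes −5.6. At d = 0.4, −3.4 becomes −11.2, and the total error with two switchers rises from 5.1% to about 6.0%. It is therefore not a remedy.

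**The case against.** The strongest reply is that nothing tells staff to mix forms. Direct interview is the default at both visits, proxy is only for inability, and over one to two months most PWD would meet the same condition twice. This is fair, and it is why the point is minor. It does not cover the PWD whose status changes, and for a PWD who starts on proxy the written rule itself can produce the switch.

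A second reply is that safeguards exist. Researchers will "follow standard protocol for conducting these measures", proxy questionnaires are filed as their own document type, and forms are checked for inconsistency across visits. A switch would probably be noticed. But no visible text says how to prevent it or how to analyse the pair.

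A third reply is that the Appendix holding the measures is not shown. This stands for two things a reader might be tempted to list as defects: that being unable to respond is not defined, and that no proxy score range is stated. Either could be in the Appendix or the instrument's standard procedure, so neither is claimed here. An instrument form would not normally settle how the SAP treats mixed pairs.

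A reader might also infer a seriously inflated false-positive rate. With four switchers in the same direction (SD 10, d = 0), the simulated total is about 9.0%. The documents give no support for that many switches, still less all one way.

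**Conclusion.** The point holds as a minor one. The self-or-proxy condition is applied separately at each visit to two different instruments, and the SAP treats the results as one scale. Any switched pair is hard to interpret, and the net direction of its error is unknown.

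The size is small: about 5.0% total two-sided error for one switcher and 5.7% for two (5.5% to 6.0% for SDs of 12 to 8), with a modest tilt between false improvement and false worsening. These figures rest on assumed values for the SD of change, the item mean and the number of switchers, on 1-to-4 scoring of both forms, and on no true change. They do not include the effect of changing the staff informant, which cannot be quantified from the documents. That a switched pair does not measure change on one scale needs none of these assumptions.

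The documents do not support reading this as a threat to the trial's main conclusion. The DEMQOL serves a secondary objective, and the SAP defines success by the MPES and EPWDS alone.

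**What to change.** **Protocol, Post-Treatment Assessments, DEMQOL item.** State that the form used at baseline is repeated, with the same proxy informant where possible. A PWD who starts on proxy stays on proxy. Only a PWD who can no longer self-report changes form, and the change is recorded. This removes proxy-to-self switches without losing any pairs.

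**SAP.** State that the main DEMQOL paired t-test uses same-form pairs. Report the number and direction of unavoidable switches, and give the all-pairs result as a sensitivity analysis.

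**Cost.** Wording only, with no added visits or interviews. Within same-form pairs the length effect is zero. The downside is selection: a PWD who declines and has to switch drops out of the main comparison. If s of 24 PWD truly declined by D points and the rest did not change, leaving them out raises the mean by sD/24. For assumed s = 1 to 2 and D = 5 to 10, that is 1 × 5/24 = 0.21 to 2 × 10/24 = 0.83 points. This is of the same order as the 0.375 to 0.75 points from form length, so the all-pairs result should always be shown beside the main one.
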